8. INVESTIGATIONAL PLAN

Research Questions

1. Does dietary supplementation of carnosine during a period of high PM_{2.5} pollution mitigate effects on vascular indices?
2. Does dietary supplementation of carnosine during a period of high PM_{2.5} pollution improve the arterial function?
3. Does dietary supplementation of carnosine during a period of high PM_{2.5} pollution decrease endothelial damage?
4. Does dietary supplementation of carnosine during a period of high PM_{2.5} pollution decrease platelet activation?

Study Design

This is a randomized, double-blind, placebo-controlled longitudinal clinical intervention study to assess whether dietary supplementation of a naturally occurring peptide in the body will mitigate the harmful effects of seasonal PM_{2.5} air pollution on indices of vascular biology. A total of 240 participants will be enrolled and randomized in 1:1 ratio to receive either dietary carnosine or placebo (cornstarch). Stratification factors are sex (birth male and female), age (22-44; 45-65) and carnosine level (very low, low). A block (or size 6) stratified randomization scheme will be used. Accounting for a conservative attrition rate of 40% (failure to complete all study time-points), a total of 400 participants will be randomized to receive either dietary carnosine supplementation or placebo (cornstarch).

The mode of dietary supplementation will be oral capsules. Intervention of dietary carnosine supplementation or placebo will occur daily, for 12 consecutive weeks during a period of high PM_{2.5} pollution – May through September. Due to logistical limitations, enrollment may be split over multiple years, but will occur during the same monthly period of high PM_{2.5} pollution (May through September) in the study region (30 miles radius from Louisville Kentucky). The 12 weeks supplementation period was selected based upon previous dietary carnosine supplementation trials as a reasonable and commonly used time frame to assess benefit and risk.^{34, 37} Based on existing literature, a measureable effect of carnosine on many indices is noticeable by 6 weeks of starting supplementation and can reach peak effect by 12 weeks.^{34, 37}

The general study enrollment and investigational plan for Year # 1 (2020) and Year # 2 (2021) is illustrated and outlined in Figure 1 and Figure 2 respectively. Details regarding each individual study visit are illustrated and outlined in Figures 3-7. The study visits and details regarding each visit are further detailed in section 10 “Study Visits”.

The study PI and other investigators will be blinded to the allocation of participants to either carnosine or placebo. The participants will also be blinded to their allocation. The Randomization Committee (RC) will be in possession of the randomization key so that accurate unblinding of the randomization assignment may be identified in the event of a medical or other Carnosine NEAT Trial Protocol
Version Date 5-14-2020

emergency. The RC will consist of four individuals: the pharmacist compounding the supplement ([name]), the study physician ([name]), a member of the UofL Clinical Trials Unit, and the study biostatistician ([name]). Study supplements (carnosine or placebo) will be prepackaged into punch cards and marked with letters "A" or "B". The contents of series "A" or "B" will be part of the blinded randomization and will be known only to the RC. The study supplements will be directly shipped, stored and handled by the UofL CTU.

An initial screening (Visit # 1) of potential / interested participants will be conducted to identify eligible candidates based on eligibility criteria established *a priori*. Eligible candidates will be invited to a complete baseline assessment (Visit # 2). Randomization and allocation will occur between Visit # 1 and Visit # 2. Participants invited for Visit # 2 will already be randomized into one of the two study groups (carnosine or placebo). Participants from both study groups will be followed up at 6 weeks (Visit # 3) and 12 weeks (Visit # 4). Relevant and extensive data for primary and secondary endpoints will be collected at Visit # 2 through Visit # 4. The data collected throughout all visits (# 1 through # 4) may be used to generate preliminary data for future studies.

Visit # 1 will focus on consenting the participant for the entire study, collect contact/demographic information, and collect a urine sample. Safety assessments will be conducted at Visit # 3 and Visit # 4. Participants may be contacted for up to 12 months after enrollment via phone/email/mail for safety, adverse events, and or general follow up questions.

Study Endpoints

Primary Endpoints (reflecting change from baseline to 6 weeks and 12 weeks and between groups)

1. Difference in EPC-2 between Carnosine and Placebo Groups
2. Difference in EPC-3 between Carnosine and Placebo Groups
3. Difference in EPC-4 between Carnosine and Placebo Groups
4. Difference in EPC-7 between Carnosine and Placebo Groups
5. Difference in EPC-8 between Carnosine and Placebo Groups

Secondary Endpoints (reflecting change from baseline to 6 weeks and 12 weeks and between groups)

1. Difference in Arterial Stiffness between Carnosine and Placebo Groups
2. Difference in Endothelial Microparticles between Carnosine and Placebo Groups
3. Difference in Platelet Monocyte Aggregates between Carnosine and Placebo Groups

Data Collection Tools

Blood Samples

A sample of ~3 table spoons (~45 ml) of blood will be obtained by venipuncture performed by a study staff trained in phlebotomy using standard procedures and precautions to insure the safety of the participants and phlebotomist. If any subject becomes ill, uncomfortable, or desires to withdraw, he/she may do so at any time. Blood sample collection protocol is detailed in Appendix A. Samples will be promptly transported to the Diabetes and Obesity Center's research laboratory on the 4th floor of the Delia Baxter building ([name]) for processing, storage, and analysis. After processing, samples will be aliquoted in appropriately labeled vials and stored in (-80C) freezer. Stored samples will contain study name, participant ID, date of sample acquisition, type of sample, and visit type. Samples will be stored in de-identified fashion and participant personal information or PHI will not be displayed/barcoded on any stored sample. Samples will be stored for future use, ancillary studies, and or preliminary data development.

The measurement of blood biomarkers for primary and secondary endpoints from blood samples (EPCs, microparticles, and PMA) are further detailed in Appendix B.

Urine Samples

Standard clean catch urine sample will be obtained from participants and stored at 4°C. Urine sample collection protocol is detailed in Appendix A. The samples will be transported on ice to the Diabetes and Obesity Center's research laboratory on the 4th floor of the Delia Baxter building ([name]) for processing, storage and mass spectrometric analysis. After processing, samples will be aliquoted in appropriately labeled vials and stored in (-80C) freezer. Stored samples will contain study name, participant ID, date of sample acquisition, type of sample, and visit type. Samples will be stored in de-identified fashion and participant personal information or PHI will not be displayed/barcoded on any stored sample. Samples will be stored for future use, ancillary studies, and or preliminary data development.

Arterial Stiffness Test (Vascular Function)

To assess CVD risk, we will acquire arterial stiffness measures (augmentation index; AI, augmentation pressure; AP, and pulse wave velocity; PWV), aortic systolic pressure and SEVR derived from pulse wave analysis using SphygmoCor, which provides highly reproducible values.³⁸⁻⁴⁰ The participant will be asked to provide the initials of their first and last name and date of birth. The device will also store the participant ID, date, and time of data acquisition. These parameters are necessary to calculate age and for data retrieval. Data will be stored on the device and other HIPAA compliant storage databases.

Measures of arterial stiffness are positively and robustly associated with increased risk for CV events,⁴¹ and are associated with atherosclerosis, hypertension, stroke, Alzheimer-type dementia, and kidney disease. They provide novel and clinically-relevant information beyond that provided by standard risk factors; have been increasingly incorporated into longitudinal cohort studies,⁴¹ and are particularly sensitive to air pollution exposure.⁴²

SphygmoCor Xcel is a class-II FDA approved device used in clinical and research settings. SphygmoCor is a non-invasive, cuff-based tool used for obtaining brachial artery blood pressure and the central arterial pressure waveform with associated indices (augmentation index, augmentation pressure, and pulse wave velocity). A cuff will be applied on the upper arm in the standard position. The cuff will be partially inflated to record the brachial waveforms. These waveforms are detected by sensing changes in the pressure inside the cuff related to arterial pulsation. The ascending aortic waveform is subsequently derived using a validated mathematical transfer function.

The participant may be provided with their current blood pressure and heart rate, as measured by this FDA approved device.

Questionnaires

Self-reported interview-style questionnaires are quick, convenient and reliable source of research data collection. This modality is used by many large NIH funded research studies like the Multi-Ethnic Study of Atherosclerosis (MESA), the National Health and Nutrition Examination Survey (NHANES), and many of our group's other NIH funded studies – the Green Heart Project, Cardiovascular Injury in Tobacco, Louisville Healthy Heart Study, etc. We will utilize these existing questionnaires (internal and external) to compile a list of relevant questions which will help in high quality data acquisition. The questionnaires will collect data on medical history, medications, environmental pollution exposure, sleep, diet, exercise, tobacco, and women's health.

Data will be recorded in real-time in a REDCap database created specifically for this study. Since, these questionnaires will collect multiple personal information and PHI, only trained research personnel with relevant reason will be granted access.

Physical Examination

[figure not shown]
Physical examination will be conducted to record the participant's height, weight, and waist circumference. Blood pressure and heart rate measurements will be provided during the arterial stiffness measurement.

Physical Function Test

To assess the impact of carnosine supplementation on physical performance during times of variable PM_{2.5} levels, we will utilize three physical performance tests: handgrip

Carnosine NEAT Trial Protocol
Version Date 5-14-2020

Page 21 of 82

strength test, 2-minute step test (2MST), and bilateral calf-raise test. The protocol for these measurements are further detailed in Appendix E.

Sample Size Computations and Assumptions

The primary outcome measures are EPC-2, EPC -3, EPC -4, EPC -7, and EPC -8. Also, there are many secondary outcome measures. Based on our pilot study, mean and SD (standard deviation) are reported below.

	EPC-2	EPC-3	EPC-4	EPC-7	EPC-8
Mean	0.675783	0.016016	0.050813	0.297092	0.631728
SD	0.702561	0.010805	0.056709	0.412414	0.691299

This is a longitudinal study and primary observations will be made at baseline, 6 weeks and 12 weeks follow-ups. Due to 5 primary outcome measures, we adjusted alpha=0.01 (=0.05/5). Due to multiple sub-studies, we plan to enroll a large evaluable cohort of size n=240. With a correlation of 0.5 on any two consecutive time-point measures, (this is a conservative estimate) and n1=120, n=120 at alpha= 0.01 and power=0.90, we can detect the effect size of 0.5 SD using a two sample t-test in a longitudinal setting. The detectable effects for each EPC is given below.

Power	Correlation	EPC-2	EPC-3	EPC-4	EPC-7	EPC-8
80%	0.50	0.351	0.005	0.028	0.206	0.346
90%	0.50	0.223	0.003	0.018	0.131	0.219
80%	0.80	0.197	0.003	0.016	0.116	0.194
90%	0.80	0.156	0.002	0.013	0.092	0.153

To adjust for attrition/drop out we have increased the sample size to 400.

Associations of PM_{2.5} exposures with measured outcomes will be estimated using mixed effects models. We will use interaction variables to detect whether the association between PM_{2.5} and outcomes is significantly different between with or without carnosine groups. We will perform a formal mediation analysis, which allows for interactions to determine the degree to which carnosine levels mediate the effect of PM_{2.5} on our outcomes. Plots of subject-specific differences over pollution concentrations along with regression plots will be generated.

Sample Size Recommendation

Sample size of 240 participants (120 carnosine supplementation, 120 placebo group) provides sufficient sample size for the primary endpoint as well as other secondary endpoints.

Due to the prolonged intervention period (12 weeks), two follow-up visits and the inconvenience of taking multiple oral capsules daily, we anticipate a 40% attrition from screening (Visit # 1) through 12-week follow-up (Visit # 4). Therefore, we have established a goal of stratified identification of a total of 400 participants (1:1) at screening (Visit # 1). We anticipate that with a conservative estimate of 60% retention, 120 participants in each group (supplementation, placebo) will complete the entire study.

Multiple Testing Issue

Type I error correction in the context of an early phase clinical trial that performs multiple tests can serve to protect the study interpretation against Type I error inflation. However, the use of corrections for multiple comparisons in “proof-of-concept-studies” is problematic. At this investigational level, tight control of the overall family-wise Type I error rate would increase the likelihood that the investigators would miss a finding of potential importance by attributing it to chance simply because the p-value is large. The study investigators have, in this protocol, attempted to balance the need to control the number of evaluations with the need to identify new effects by not incorporating a multiplicity correction. The primary outcomes measures will be declared significant for alpha <0.01. There will not be any adjustments for secondary outcome measures and will be declared significant at alpha <0.05.

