10. STUDY VISITS

Screening (Visit # 1)

The screening period extends from the date informed consent is signed until the day of randomization (Figure 3). The screening window will not exceed 180 days prior to randomization.

The following activities will be carried out at screening:

1. Informed Consent (for entire study)
2. Blood and or Urine sample collection
3. Demographic data
4. Contact information
5. Prepaid \$25 VISA gift card

Participants may be excluded from the study if any of the above screening data collection is not completed or meets an exclusion criterion during the screening period. Data gathered from screening (Visit # 1) will be used to identify whether the candidate meets the enrollment criteria for the main study and whether they are eligible to be randomized. Eligible candidates will be invited to participate in the main study and subsequently randomized in a double blind fashion.

Baseline Assessment (Visit # 2)

Baseline assessment will occur after eligible candidates have been identified via screening (Visit # 1) (Figure 4). Participants attending the baseline assessment (Visit # 2) will already be randomized into carnosine or placebo group. Participants will be provided with the study supplement during this visit and they will start their dietary supplement regimen (carnosine or placebo) immediately on the day of baseline assessment. The following activities will be carried out at Baseline Assessment:

1. Update Demographics and Contact Information
2. Questionnaire data on Medical History, Medications, Exposure to Environmental Pollution, Sleep, Diet, Exercise, Tobacco, and Women's Health
3. Blood sample collection (~3 tablespoons or ~45ml)
4. Urine sample collection (~2 tablespoons or ~30ml)
5. Arterial stiffness test (SphygmoCor)
6. Physical strength test (hand grip test, step test, calf raise test)
7. Provide 8 weeks of study dietary supplement capsules (carnosine or placebo)
8. Discuss schedule and related instructions related to taking the study dietary supplement
9. Prepaid \$50 VISA gift card

Participants may be excluded from the study if any of the above data collection is not completed or meets an exclusion criterion during this period.

Follow-Up # 1 (Visit # 3)

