Participants may be excluded from the study if any of the above data collection is not completed or meets an exclusion criterion during this period.

4 – 12 Month Safety Check (Visit # 5)

Although this interaction is termed as a “Visit”, it will not involve participants to physically be present. A follow-up email / phone call / mailed paper questionnaire will be conducted 4-12 months after the end of supplement intervention (Figure 7). This contact will focus on updating about any SAEs & medical / medication history changes since end of intervention:

1. Update Demographics and Contact Information
2. Questionnaire data on Medical / Medications History since end of intervention
3. Questionnaire data on adverse effects or SAEs since end of intervention.
4. No monetary compensation for this follow-up / check.

Participants will not be excluded from the study if any of the above data collection is not completed. Instead, they will be categorized as “lost to safety follow-up”.

Safety Evaluations during Study Visits

Adverse events will be assessed during Visit # 3 and Visit # 4 and through the 12 months after participants have stopped taking study supplement. The following will be documented in the adverse event reporting system:

1. **Local reactions:** diarrhea, stomach upset, tingling sensation in extremities, rash or itchiness, dry mouth, changes in appetite, feelings of tiredness, or vivid dreams.
2. **Systemic reactions:** fever, allergic reaction, anaphylaxis or any clinical untoward event that occurs within 30 days of beginning study supplement.
3. **Abnormal laboratory results** which are deemed clinically significant.
4. **Pregnancy and breast-feeding:** Currently, there is not enough reliable information about the safety of taking carnosine supplement during pregnancy or breast-feeding. Hence, participants/candidates who are currently pregnant or breast-feeding or plan to be pregnant/breast-feeding during the study period will be “discontinued” from the study.

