12. CLINICAL AND LABORATORY EVALUATIONS

Schedule of Procedures

Study Activities	Screening (Visit # 1)	Screening (Visit # 2)	Screening (Visit # 3)	Screening (Visit # 4)	4-12 Month Safety Check
Informed Consent	X				
Contact & Demographics	X	X	X	X	
Medical History		X	X	X	X
Medications History		X	X	X	X
Physical Exam		X	X	X	
Blood Samples		X	X	X	
Urine Samples	X	X	X	X	
Arterial Stiffness Exam		X	X	X	
Physical Function Exam		X	X	X	
Environmental Pollution Exposure Questionnaire		X	X	X	
Sleep Questionnaire		X	X	X	
Diet & Exercise Questionnaire		X	X	X	
Supplement Distribution		X	X		
Adverse Events Check			X	X	X
Checkout (Prepaid Visa)	X	X	X	X	

Procedure Details

Contact and Demographics

A detailed account of the participant's contact and demographic information will be collected at screening (Visit # 1). This information will be critical while implementing the screening criteria and selecting eligible candidates for randomization. This information is also required for NIH progress report reporting. It will be administered by a research team member at every clinical study visit (Visit # 1 through # 4).

Participant Medical History and Physical Exam

A complete participant history including medical, alcohol, tobacco, and medication review will be conducted at baseline assessment (Visit # 2).

A complete physical exam including vitals, height, and weight will be completed at baseline assessment (Visit # 2). Similar physical exams will be conducted at each additional clinic visit (Visit # 3 and Visit # 4) during the study.

Blood and Urine Samples

[figure not shown]
A fresh catch urine sample will be collected at screening (Visit # 1). Urine sample collection details are in Section 8 “Investigational Plan” and Appendix A. This is necessary to identify the candidate’s body carnosine level and to implement the inclusion criteria. This information is critical in screening and selecting eligible candidates for randomization. A fresh catch urine sample will be collected by a research team member at every clinical study visit (Visit # 1 through # 4).

Fresh stick blood samples will be collected at baseline assessment (Visit # 2). Blood sample collection details are in Section 8 “Investigational Plan” and Appendix A. Fresh stick blood samples will be collected at each additional clinical study visit from baseline onwards (Visit # 2 through Visit # 4).

Arterial Stiffness Test

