Hospitalization does not include rehabilitation facilities, hospice facilities, respite care (i.e., caregiver relief), skilled nursing facilities or homes, routine emergency room admissions, or same day surgeries (as outpatient/same day/ambulatory procedures). Hospitalization or prolongation of hospitalization in the absence of a precipitating, clinical AE/SAR is not in itself an SAE/SSAR.

Unanticipated Problems (UPs)

An UP is an incident, experience, or outcome that specifically causes increased risk to the study or to its participants which may be of medical or non-medical etiology, and meets the following criteria:

1. Unexpected (in terms of nature, severity, or frequency), given (a) the research procedures that are described in the protocol-related documents, such as the IRB-approved research protocol and informed consent document; and (b) the characteristics of the subject population being studied
2. Definitely, probably, or possibly related to participation in the research (i.e., there is a reasonable possibility that the incident, experience, or outcome may have been caused by the procedures or materials involved in the research); and
3. Suggests that the research places participants or others at a greater risk of harm (including physical, psychological, economic, or social harm) than was previously known or recognized
4. All UP reporting will follow the same guidelines as noted above for SAE/SSAR reporting, and must include a corrective action plan/measures to prevent recurrence.

Reporting by Principal Investigator

For all events (AE/SAR and SAE/SSAR), monitoring and reporting to the PI or EC begins at the time that the participant provides informed consent, which is obtained prior to the participant's participation in the study, i.e., prior to undergoing any study related procedure and/or receiving study supplement, through and including 30 calendar days after the subject completes the study. Events should be recorded on the Adverse Event electronic case report form (eCRF). Do not delay the initial reporting of an event in order to obtain resolution or follow up information.

For all events, the PI must pursue and obtain adequate information both to determine the severity and causality of the event. For events with a causal relationship to the study supplement, follow-up by the Investigator is required until the event or its sequelae resolve or stabilize at a level acceptable to the PI, who concurs with that assessment.

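### No structured pre-dose record of the common symptoms is specified, and the scheduled adverse-event check starts only at Visit 3, so old complaints can be mistaken for new events

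*Combined protocol and SAP*

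**What the plan says.** **When events are asked about.** Section 8 (Study Design) states: "Safety assessments will be conducted at Visit # 3 and Visit # 4". Section 10 (Safety Evaluations during Study Visits) agrees: "Adverse events will be assessed during Visit # 3 and Visit # 4 and through the 12 months after participants have stopped taking study supplement". The row "Adverse Events Check" in the Section 12 schedule is marked at Visit 3, Visit 4 and the 4-12 month contact, and Table 3 in Section 18 matches it. Neither marks Visit 1 or Visit 2.

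**When dosing starts.** At Visit 2 participants receive the capsules and, per Section 10, "they will start their dietary supplement regimen (carnosine or placebo) immediately on the day of baseline assessment". Visit 3 follows at 6 weeks, give or take one.

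**What is recorded.** Section 10 lists the local reactions as "diarrhea, stomach upset, tingling sensation in extremities, rash or itchiness, dry mouth, changes in appetite, feelings of tiredness, or vivid dreams". That item carries no condition of onset or worsening. The next item, on systemic reactions, does have a time limit of 30 days from starting the supplement.

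**When monitoring is meant to start.** Section 13 (Reporting by Principal Investigator) says that "monitoring and reporting to the PI or EC begins at the time that the participant provides informed consent", which is before Visit 2.

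**The concern.** The listed local reactions are everyday complaints, and people with controlled diabetes or hypertension are eligible (Section 9). Some participants may therefore have one of these symptoms on the day they start. If nothing structured is written down that day, someone at Visit 3 must decide from memory whether the complaint is old or new. Where the investigator cannot tell whether the supplement caused an event, Section 13 (Causality Assessment) handles it as possibly related.

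Two uses of the data are exposed. One is any comparison of symptom rates by arm; Section 13 itself names an aggregate excess over a concurrent control group as evidence of causality. The other is the holding criterion in Section 14 for diarrhea, vomiting or stomach upset. It is a share of total enrollment pooled over arms, with no baseline reference.

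**Working it through.** **1. Denominators.** The plan's sample size reproduces. With a 0.5 SD effect, alpha 0.01 (two-sided assumed) and 90% power, n per arm = 2(2.576 + 1.282)² / 0.5² = 119.1, so 120. Allowing for 40% attrition, 240 / (1 - 0.40) = 400. These figures are not disputed and serve only as denominators below.

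**2. Pre-dose steps that could capture the symptoms.**

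| Step | What is specified | Gap |
|---|---|---|
| Screening (Section 10) | Consent, sample, demographics, contact details | No symptom item |
| Special exclusions (Section 9) | The same local reactions, as grounds on which a candidate may be excluded | Discretionary; no form or threshold |
| Visit 2 (Sections 10, 12) | Medical history, medications, exposure, sleep, diet, exercise, tobacco and women's health questionnaires; physical exam | No checklist of the listed reactions stated |
| Section 13 | Event monitoring from consent | No scheduled check before Visit 3 carries it out |

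**3. Effect on a between-arm contrast.** The documents give no symptom rates, so all rates here are assumptions. Let b be the share with the symptom before dosing who go on to report it, o the new background onset over 12 weeks, and e the extra risk from carnosine.

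- All reports: placebo 1 - (1-b)(1-o); carnosine 1 - (1-b)(1-o)(1-e). The difference is (1-b)(1-o)e.
- New onset, among the n(1-b) people free of the symptom at Visit 2: placebo o; carnosine 1 - (1-o)(1-e). The difference is (1-o)e.

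Counting old complaints therefore multiplies the risk difference by (1-b). With b = 10% and e = 10%, a two-sided Fisher exact test at 0.05 (exact enumeration) gives:

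| New onset o | All reports, carnosine v placebo | New onset only | Power at 120 per arm, without → with baseline check |
|---|---|---|---|
| 2% | 20.6% v 11.8% | 11.8% v 2.0% | 39% → 79% |
| 10% | 27.1% v 19.0% | 19.0% v 10.0% | 27% → 40% |
| 20% | 35.2% v 28.0% | 28.0% v 20.0% | 19% → 23% |

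With o held at 2%, power goes from 54% to 82% at b = 5%, and from 24% to 72% at b = 20%. At 200 per arm with b = 10% and o = 2%, it goes from 62% to 96%.

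**4. Effect on the holding count.** The criterion is 20% × 400 = 80 people. Let p be the new-onset risk in an arm, so that the counted risk is b + (1-b)p. Assume p = 5% on placebo and 15% on carnosine, with every old complaint counted. The pooled risk and the binomial chance of at least 80 in 400 are:

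| b | Pooled risk | Chance of reaching 80 |
|---|---|---|
| 0% | 10.0% | about 0% |
| 5% | 14.5% | 0.2% |
| 10% | 19.0% | 32% |
| 20% | 28.0% | over 99% |

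At b = 10%, other onset assumptions move the 32% to 12% (5% v 12%) or 96% (10% v 20%). If only new onsets are counted, the chance stays at or below 0.4% in every case run.

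**The case against.** Three stronger readings are tempting, and the documents do not support them.

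**That the plan counts old complaints as events.** It does not say so. Section 13 defines an adverse event through association in time with supplement use and offers an unrelated category where there is none. At Visits 3 and 4 staff are to discuss side-effects and health changes during the study, and to update the medical history taken at Visit 2. All of this points toward change. What remains is that no new-or-worse rule is written and no baseline symptom list exists to apply one to.

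**That nothing is asked before dosing.** Visit 2 takes a full history and several questionnaires whose items are not reproduced, and applying the Section 9 exclusion would require asking about these very symptoms. Some enquiry is likely. It is not specified as a record, however, and the exclusion is optional.

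**That a large loss of power is established.** Section 15 contains no between-arm adverse-event test. The large gain depends on 2% new onset, which is low for everyday complaints; at 20% the gain is four points. The calculation also covers only people symptom-free at Visit 2, so it does not evaluate worsening.

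Two further points count against the size. Grade 1 events are not entered in the electronic CRF (Section 13), so many mild complaints may never reach that record, although Section 10 says the local reactions will be documented in the reporting system. The stopping boundary in Section 15 uses only grade 3 or 4 events and is little affected. Participants can also contact the study team before Visit 3, so recall at that visit is not the only route.

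**Conclusion.** The gap is real but modest. Following the schedules as written leaves no structured pre-dose record of the Section 10 symptoms, and such a record cannot be rebuilt once dosing has begun. Sections 8, 10, 12 and 18 also do not carry out the start at consent stated in Section 13.

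Randomisation should spread old complaints evenly. The result is attenuation and added noise in a carnosine-placebo contrast, not a spurious difference between arms. The holding count has no such protection, because it is pooled and has no baseline reference.

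The direction follows from the algebra; the size cannot be fixed from the documents. It rests on assumed prevalence, onset and carnosine effect, and on old complaints being reported and counted. The holding probabilities are an upper-end illustration for that reason.

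**What to change.** - At Visit 2, before the first capsule, record the Section 10 local reactions with severity, using the same checklist as at Visits 3 and 4. Mark it in the Section 12 schedule and in Table 3.
- Define, and tabulate by arm, symptoms that are new or worse than at Visit 2, with all reports alongside.
- State where mild responses are kept, since Grade 1 events stay out of the electronic CRF and the comparison needs them at every visit.
- Reconcile the timing in Sections 8, 10, 12 and 18 with the start at consent in Section 13.
- State whether the Section 14 holding count refers to baseline. That choice belongs to the sponsor and the monitoring board; the Visit 2 record makes either option workable.

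The cost is about 5 minutes at an existing visit, going by the time that Table 4 allots to the check at Visits 3 and 4, plus one table definition. No new visit or sample is needed.
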